Safety: Frequencies and percentages of subjects with AEs and SAEs will be summarized by dose group. Vital signs, ECGs, laboratory evaluations, and physical examination findings will be summarized with descriptive statistics by dose group. Additional serum samples will be taken and stored for possible exploratory analyses that may be necessary to further explore any unexpected safety or tolerability observations.

PK: Individual subject TRL345 serum concentrations and derived PK parameters will be summarized using descriptive statistics.

Immunogenicity: Anti-TRL345 antibodies will be summarized with descriptive statistics by DG.

PD: Serum samples will be taken and evaluated for *ex vivo* PD assessments.

SCHEDULE OF EVENTS

Study Day	Screening	1	2	3	8	15	29	43	76
Study Week					1	2	4	6	11
Window (days)	-8 (+/-6)	-1	0	0	± 1	± 3	± 3	± 3	± 5
Visit Type	A	RU	RU	RU	A	A	A	A	A
Procedure									
Informed Consent	X								
Eligibility	X	X ¹							
Demographics	X								
Medical/Disease History	X								
Complete Physical Exam	X								
Targeted Physical Exam		X ¹	X	X	X	X	X	X	
Vital Signs ²	X	X ³	X	X	X	X	X	X	
Weight	X	X ¹						X	
Height	X								
12-Lead ECG in triplicate ⁴	X	X			X				
Laboratory Tests									
Serum Chemistry ⁵	X	X ¹	X	X	X	X	X	X	
Hematology	X	X ¹	X	X	X	X	X	X	
Amylase, lipase, creatine kinase ⁶		X ¹		X	X	X			
Fasting glucose	X	X ¹		X	X	X	X	X	
HbA1C	X								
Fasting blood insulin level		X ¹		X	X	X	X	X	
Additional serum sample for possible exploratory analyses ⁷		X ¹		X	X	X	X	X	
NT-proBNP, IL-1 α		X ¹		X		X	X	X	
CMV Serology ⁸	X								
Serum Pregnancy Test (WOCBP)	X							X	
HIV, Hepatitis B, C Serology	X								
Urine Drug Test	X								
Randomization		X ¹							
Dosing of IP (TRL345 or placebo)		X							
PK sampling – serum ⁹		X	X	X	X	X	X	X	X
PD sampling – serum ¹⁰		X				X	X	X	X
ADA sampling – serum ¹¹		X ¹			X		X	X	X
Adverse Events		X	X	X	X	X	X	X	X
Concomitant Medications		X ¹	X	X	X	X	X	X	X
Overall Status								X	X

Visit Type: A = ambulant, RU = Research Unit, NA = phone call

- To be performed prior to the administration of IP.
- Vital signs include temperature, blood pressure, and heart rate. Vital signs should be obtained after subject is resting for 5 minutes. The window for all vital signs is ± 10 minutes.
- On Day 1, vital signs will be obtained within 60 minutes prior to dosing, at 15, 30, and 60 minutes (end of the infusion), and 1 hour and 4 hours after the end of the infusion.

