4. Subjects may not use tobacco or nicotine within 4 hours prior to the ECG. ECG on Day 1 will be performed within 4 hours after completion of the infusion.
5. Serum chemistry at Days 1, 15, and 29 is to include hsCRP and LDH.
6. Subjects must refrain from strenuous exercise within 5 days prior to assessment of creatine kinase
7. An additional 5 mL serum sample will be collected immediately prior to the IP infusion on Day 1 and on Days 3, 8, 15, 29, and 43 and stored for possible exploratory analyses.
8. An established ELISA assay available in commercial laboratories to detect IgG antibodies against CMV will be used to determine serostatus of subjects.
9. Samples for PK will be collected immediately prior to the IP infusion on Day 1 and end of the infusion (60 minutes) \pm 15 minutes, and hours 2 \pm 15 minutes, 4 \pm 15 minutes, 6 \pm 15 minutes, 12 \pm 1 hour, 24 (Day 2) \pm 1 hour, and 48 (Day 3) \pm 1 hour after start of infusion and then on Days 8, 15, 29, 43, and 76.
10. Samples for PD will be collected immediately prior to the IP infusion on Day 1 and end of the infusion (60 minutes) \pm 15 minutes and on Days 15, 29, 43, and 76 for *ex vivo* PD assessments.
11. Samples for ADA will be collected immediately prior to the IP infusion on Day 1 and on Days 8, 29, 43, and 76. ADA samples collected on Days 8 and 29 will be held for exploratory analysis, if warranted.

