2.2 Endpoints

2.2.1 *Safety Endpoints*

- Incidence and severity of abnormal physical exam findings, serum chemistries and hematology, vital signs (temperature, blood pressure, heart rate), adverse events, and incidence of serious adverse events

2.2.2 *Pharmacokinetics*

- C_{max} , C_{min} , CL, Vss, and T1/2 overall and by DG will be determined by ELISA

2.2.3 *Immunogenicity*

- Incidence of baseline and IP-emergent ADA (i.e., anti-TRL345 antibodies) in serum will be determined by ELISA

2.2.4 *Pharmacodynamics*

- The proportion of samples with TRL345 concentrations within prespecified ranges that are associated with neutralization of HCMV in human serum

2.2.5 *Exploration of Possible Off-Target Binding*

- Gastrointestinal and CNS adverse events will be compared across DGs for any qualitative or quantitative differences in such events. LDH, hsCRP, IL-1alpha, estimated AUC, and estimated T1/2 will also be compared across DGs.

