6.1 Definitions and Descriptions of Assessments and Procedures

Medical history – medical history will be obtained by way of subject interview and medical records. All clinically significant past and current medical history will be obtained. Clinically significant history includes those illnesses/diagnoses that are/were treated with medication for more than 14 days or other medical intervention (e.g., hospitalization, surgery, physical therapy, etc.).

Complete physical exam – examination of the following systems: ear, nose, and throat; cardiovascular; respiratory; gastrointestinal; musculoskeletal; dermatological; neurological; and confirmation of venous access.

Targeted physical exam – brief, focused examination of the subject following medical history, including assessment for AEs.

12-lead ECG – after a subject has been supine for 5 minutes, triplicate ECGs will be obtained over 5 minutes. The investigator will interpret the ECG using 1 of the following categories: normal, abnormal but not clinically significant (NCS), or abnormal and clinically significant (CS). QTcF will also be determined. Subjects may not use tobacco or nicotine within 4 hours prior to the ECG.

Vital Signs – temperature, heart rate, blood pressure. Heart rate and blood pressure should be obtained after subject is resting for 5 minutes. Height will be obtained at Screening only. Weight will be obtained at Screening, on Day 1, and at Day 43.

Serum chemistry – sodium, potassium, chloride, carbon dioxide (CO₂), urea nitrogen (BUN), creatinine (CREA), calcium, glucose, total protein, albumin, total bilirubin, alkaline phosphatase, aspartate aminotransferase (AST), alanine aminotransferase (ALT). HsCRP and LDH will be assessed at Days 1, 15, and 29 only.

Hematology – hemoglobin, red blood cell count, white blood cell count with differential, platelet count.

Hemoglobin A1c – whole blood sample at Screening

Additional safety assessments – amylase, lipase, creatine kinase, NT-proBNP, IL-1 α , fasting glucose, fasting blood insulin. Subjects must refrain from strenuous exercise within 5 days prior to assessment of creatine kinase.

CMV serology – an established ELISA assay available in commercial laboratories to detect IgG antibodies against CMV will be used to determine serostatus of subjects.

Urine drug test – amphetamines (includes methamphetamines and ecstasy/methylenedioxymethamphetamine), barbiturates, benzodiazepines, cannabinoids, cocaine

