6.4.4 Study Days 15 (± 2 days) and 29 (± 3 days)

The following procedures will be performed:

Targeted physical exam

Vital signs

Laboratory Evaluations:

- Serum chemistry (including hsCRP and LDH)
- Hematology
- Amylase, lipase, and creatine kinase (subjects must refrain from strenuous exercise within 5 days prior to assessment of creatine kinase) (Day 15 only)
- Fasting glucose
- Fasting blood insulin level
- NT-proBNP and IL-1 α

- Serum for PK, PD, ADA, and possible exploratory analyses (ADA at Day 29 to be held for exploratory analysis, if warranted)

AE assessment

Concomitant medication assessment

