## **8. SAFETY**

All relevant case report form (CRF) and clinical laboratory data will be listed by subject and chronologically by assessment time point. This will include rechecks, unscheduled, and early termination assessments.

Applicable continuous variables will be summarized using n, mean, SD, minimum, median, maximum, and range. Data from subjects who received the placebo treatment will be pooled across dose groups.

The level of precision will be presented as follows: minimum/maximum/range in the same precision as in the database, mean/median in one more precision level than minimum/maximum/range, SD in one more precision level than mean/median, and n will be presented as an integer. Percentages will be presented as an integer.

Where individual data points are missing because of dropouts or other reasons, the data will be summarized based on reduced denominators.

Baseline will be the result closest and prior to start of dosing unless otherwise stated. Summaries for post-baseline time points will not include rechecks, unscheduled, or early termination measurements.

Tables summarizing safety data by assessment time point will only include summaries for baseline and post-baseline time points.

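### The exercise restriction covers LDH at baseline and Day 15 but not at Day 29, adding avoidable noise to a marker named for the off-target comparison

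*Protocol*

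**What the plan says.** Footnote 6 of the Schedule of Events, attached to the row "Amylase, lipase, creatine kinase", sets the restriction: "Subjects must refrain from strenuous exercise within 5 days prior to assessment of creatine kinase". Section 6.1 and the visit lists in Sections 6.4.1 to 6.4.4 repeat it, always attached to creatine kinase. Section 5.9 (Other Study Restrictions) deals only with birth control, and the eligibility criteria say nothing about exercise.

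The creatine kinase row is marked on Days 1, 3, 8 and 15. For the combined Day 15 and Day 29 visit list, Section 6.4.4 has: "Amylase, lipase, and creatine kinase (subjects must refrain from strenuous exercise within 5 days prior to assessment of creatine kinase) (Day 15 only".

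LDH follows a different calendar. Footnote 5 says: "Serum chemistry at Days 1, 15, and 29 is to include hsCRP and LDH". Section 6.1 confirms it: "HsCRP and LDH will be assessed at Days 1, 15, and 29 only".

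LDH is more than a routine panel item here. Protocol Section 2.2.5 states: "LDH, hsCRP, IL-1alpha, estimated AUC, and estimated T1/2 will also be compared across DGs", and SAP Section 2 repeats this. SAP Section 8.5 puts LDH in the chemistry tables, with descriptive statistics and change from baseline by time point and treatment. SAP Section 8 defines the reference value: "Baseline will be the result closest and prior to start of dosing unless otherwise stated".

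**The concern.** The protocol controls exercise before creatine kinase draws but does not extend that control to LDH. Because the first two LDH draws coincide with creatine kinase draws, they happen to be covered. The third does not coincide and is not covered.

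LDH has only two post-dose values, Day 15 and Day 29. Change from baseline at Day 15 compares like with like. At Day 29 it sets a sample taken under no restriction against a baseline taken under restriction, so a rise within a group could come partly from exercise. With 6, 6 and 4 subjects, one or two people who exercised hard before the visit could move a group mean enough to suggest, or obscure, a difference between groups in an exploratory comparison meant to pick up off-target binding.

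**Working it through.** The documents give no figure for this point, so there is nothing to reproduce. The check has two parts: the calendar, and an illustration of size.

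**Calendar** (Schedule of Events; Sections 6.1 and 6.4.1 to 6.4.4)

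| Study day | Creatine kinase, hence restriction | LDH |
|---|---|---|
| 1 (pre-dose) | yes | yes |
| 3 | yes | no |
| 8 | yes | no |
| 15 | yes | yes |
| 29 | no | yes |

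LDH days {1, 15, 29} minus creatine kinase days {1, 3, 8, 15} leaves {29}.

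Visit windows do not close the gap. The last restriction ends with the Day 15 draw, at the latest on Day 17 (±2 days, Section 6.4.4) or Day 18 (±3 days, Schedule of Events; the two windows differ, but the result is the same). The earliest Day 29 visit is 29 − 3 = Day 26, and the 5 days before it begin on Day 26 − 5 = Day 21. The two periods cannot overlap.

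**Size** (assumed inputs; the documents give none)

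Let p be the share of unrestricted subjects who exercise hard in the 5 days before Day 29, taken as 10% to 30%. Let r be the proportional rise in LDH in those subjects, taken as 20% to 50%. Subjects are treated as independent, with the same p in every group. Group sizes are 6 and 6 on TRL345 and 2 + 2 = 4 on pooled placebo.

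- Expected shift within any group = p × r. Low: 0.10 × 20% = 2%. High: 0.30 × 50% = 15%. The same shift is expected in all three groups, so the expected difference between groups is zero.
- Chance of at least one exerciser = 1 − (1 − p)^n. For n = 6: 1 − 0.9^6 = 47% to 1 − 0.7^6 = 88%. For n = 4: 1 − 0.9^4 = 34% to 1 − 0.7^4 = 76%.
- Chance that the two TRL345 groups contain different numbers of exercisers = 1 − Σ P(X = k)², with X binomial(6, p): 58% at p = 0.10 and 75% at p = 0.30.
- SD of the exercise-induced difference in group means = r × √(p(1 − p)) × √(1/n₁ + 1/n₂).
  - TRL345 groups, 6 against 6: 20% × 0.300 × 0.577 = 3.5%, to 50% × 0.458 × 0.577 = 13.2%.
  - TRL345 group against pooled placebo, 6 against 4: 20% × 0.300 × 0.645 = 3.9%, to 50% × 0.458 × 0.645 = 14.8%.

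**The case against.** The strongest reply is that the endpoint is a comparison across groups, and on Day 29 every group is unrestricted to the same degree, including the concurrent blinded placebo subjects. A reader might infer that the off-target comparison is biased. The design does not support that: with the same exercise rate in each group the expected difference is zero, and the 2% to 15% shift belongs to placebo as much as to TRL345. This part of the reply stands in full. What remains is noise between groups and a mixed meaning for within-group change.

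A reader might also infer that a raised Day 29 LDH could not be explained because no creatine kinase is scheduled that day. That goes too far. Section 7.3 calls for a repeat test to confirm a clinically significant abnormality and for further tests to establish its cause when clinically indicated. Footnote 7 has an extra 5 mL of serum stored on Day 29, and Section 6.5 allows stored samples to be used for additional safety laboratory tests, so a same-day creatine kinase is possible. SAP Section 8.5 lists out-of-range values and rechecks by subject, so an individual outlier would be seen. These routes can explain a rise after the event; they do not make the Day 29 sample comparable with baseline.

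Third, the documents link exercise to creatine kinase only, and the assumed rates have no anchor in them. This also stands: the Day 29 samples are unrestricted, which does not show that any of them is affected.

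Finally, no planned decision turns on this value. The Safety Monitoring Committee's escalation review uses data through Day 15, where LDH and creatine kinase are paired, and no pausing criterion names LDH.

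**Conclusion.** The point holds as a minor design improvement. The mismatch in sampling conditions is certain from the schedule: one of the two post-dose LDH values is collected without the restriction that covers its baseline. The consequence is modest. Day 29 change from baseline within a group may include exercise, and the comparison across groups carries avoidable noise, with an SD of about 3.5% to 13% between the TRL345 groups and about 4% to 15% against pooled placebo.

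Those figures rest on the assumed 10% to 30% exercise rate, the assumed 20% to 50% rise, compliance with the restriction at Days 1 and 15, and the general physiology that LDH also comes from muscle. The documents give no LDH variability, so how this compares with ordinary variation between subjects cannot be said.

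The reasoning could be stretched to AST, which is in the same chemistry panel, and so to Day 43. The documents do not support that on this ground: AST is not among the markers in Section 2.2.5, and no LDH is drawn on Day 43.

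**What to change.** Reword footnote 6 and Section 6.4.4 so that the existing 5-day restriction applies before every post-screening visit at which creatine kinase or LDH is drawn, and align the matching sentence in Section 6.1. Because LDH on Days 1 and 15 is already covered, this adds Day 29 only. It puts all three LDH values under the same condition.

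The cost is a sentence in each place and one more short activity restriction for subjects. No sample, procedure or analysis is added. The change does not schedule a creatine kinase on Day 29, so an unexpected LDH rise would still be pursued through Section 7.3 or the stored serum. If the sponsor prefers to leave the schedule alone, the report should state that Day 29 LDH was collected without the restriction when the off-target comparison is interpreted.

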5.4 Administration of Investigational Product

IV administration of TRL345/placebo will be performed by **blinded**, trained, and qualified site personnel. A calibrated IV infusion pump will be set to deliver the total volume of IP over a 60-minute period. Start and stop times will be recorded in the subject record and eCRF.

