5.7 Management of Infusion Reactions

It is required that all sites have the personnel, equipment, and medications to manage hypersensitivity reactions. Subjects must be monitored closely for signs and symptoms of an infusion reaction (IR) (e.g., fever $>38^{\circ}\text{C}$ (100.4°F), chills, flushing, bradycardia, hyper- or hypotension, itching, flushing urticaria, nausea, vomiting, abdominal pain, chest tightness, angioedema, or respiratory distress). In the event of an IR, the infusion should be slowed or stopped and restarted at the discretion of the Investigator. If a severe IR occurs (Grade 3 or 4 signs or symptoms), discontinue infusion and institute treatment as appropriate. Any infusion-related adverse event will be reported to the SMC within 24 hours.

In addition, if a subject experiences a severe IR, the following procedures will be undertaken:

- A targeted physical examination to capture medically relevant details, including but not limited to, a thorough dermatologic examination; a chest examination for breath sounds, stridor or wheezing; and a cardiac examination with attention to irregular heartbeat.
- Vital signs (sitting or supine blood pressure, heart rate, and body temperature) will be captured at the time of the IR and at least every 15 minutes until the resolution or stabilization of the IR. In addition, hematology and serum chemistry will be taken.

The Investigator may administer any medically indicated pharmacologic agent or procedure intended to relieve symptoms. Signs and symptoms of the IR and drugs given for treatment are to be recorded in the medical record and in the separate electronic case report form (eCRF) page for possible and probable IRs.

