6.4 On-Study Procedures

6.4.1 Study Day 1

The following procedures will be performed prior to administration of IP:

Reconfirm eligibility

Targeted physical exam

Concomitant medication assessment

Laboratory Evaluations, including:

- Serum chemistry (including hsCRP and LDH)
- Hematology
- Amylase, lipase, and creatine kinase (subjects must refrain from strenuous exercise within 5 days prior to assessment of creatine kinase)
- Fasting glucose
- Fasting blood insulin level
- NT-proBNP and IL-1 α
- Serum for PK, PD, ADA, and possible exploratory analyses (see additional times below for PK and PD)

The following procedures will be performed at the times specified below:

Vital signs within 60 minutes prior to dosing and then at 15, 30, and 60 minutes (end of the infusion), and 1 and 4 hours after the end of the infusion

Serum for PK will be obtained at prior to the start of infusion and then at end of infusion (60 minutes), and 2, 4, 6, 12, 24 (Day 2), and 48 hours (Day 3) after the start of the infusion

Serum for PD will be obtained at prior to start of infusion and then at end of infusion (60 minutes)

12-lead ECGs in triplicate within 4 hours post-completion of infusion (subjects may not use tobacco or nicotine within 4 hours prior to the ECG)

Additionally, the following will be performed:

Randomization of the subject to study/DG

Intravenous dosing of study IP per randomization assignment. A calibrated IV infusion pump will be set to deliver the total volume of IP over a 60-minute period.

Adverse events will be assessed during and after the infusion.

6.4.2 Study Days 2 and 3

The following procedures will be performed:

Targeted physical exam

Vital signs

Laboratory Evaluations, including:

- Serum chemistry
- Hematology
- Amylase, lipase, and creatine kinase (subjects must refrain from strenuous exercise within 5 days prior to assessment of creatine kinase) (Day 3 only)

- Fasting glucose (Day 3 only)
- Fasting blood insulin level (Day 3 only)
- Additional serum sample for possible exploratory analyses (Day 3 only)
- NT-proBNP and IL-1 α (Day 3 only)
- Serum for PK

AE assessment

Concomitant medication assessment

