### **6.3 Pharmacokinetic Concentrations**

#### **Measurements and Collection Schedule**

Blood samples for the determination of TRL345 in serum will be collected for all subjects at the following time points:

- Day 1: Predose (imputed as time 0) and approximately 1 hour  $\pm$  15 minutes (end of infusion [EOI]), 2 hours  $\pm$  15 minutes, 4 hours  $\pm$  15 minutes, 6 hours  $\pm$  15 minutes, and 12 hours  $\pm$  15 minutes post-start of infusion (SOI)
- Days 2 (24 hours  $\pm$  1 hour post-SOI), 3 (48 hours  $\pm$  1 hour post-SOI), 8 (168 hours post-SOI), 15 (336 hours post-SOI), 29 (672 hours post-SOI), 43 (1008 hours post-SOI), and 76 (1800 hours post-SOI)

All concentration data, as received from the bioanalytical lab, will be listed by subjects, treatment, and nominal time in an appendix. If there are any significant protocol deviations (e.g., significant time deviations from nominal sample times), some individual concentration data may be excluded from mean data presentations (e.g., descriptive statistics for concentrations at specific nominal time points and mean concentration-time plots). No concentration values will be imputed for missing or not reported samples (NS or NR), unless predose. All deviations and excluded data will be provided and discussed in the CSR.

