**Table 6–1 Noncompartmental Serum TRL345 Pharmacokinetic Parameters to be Calculated**

Parameter	Label to be Used in the Text, Tables, and Figures*	Definition	Method of Determination
AUC 0-tlast	AUClast	Area under the concentration-time curve from time 0 to the time of the last observed/measured non-zero concentration	Calculated using the Linear Trapezoidal with Linear Interpolation Method
AUC 0-inf	AUC0-inf	Area under the concentration-time curve from time 0 extrapolated to infinity	Calculated as $AUC_{0-inf} = AUC_{0-tlast} + (C_{last}/K_{el})$ where Clast is the last observed/measured concentration
AUC%extrap	AUC%extrap	Percent of AUC0-inf extrapolated	Calculated as $AUC\%extrap = (1 - (AUC_{0-tlast}/AUC_{0-inf})) \times 100$
C coi	Ccoi	Concentration at the end of infusion	Taken directly from bioanalytical data
C min	Cmin	Minimum observed concentration following a single dose corresponding to the single IV dose administration	Taken directly from bioanalytical data
C max	Cmax	Maximum observed concentration	Taken directly from bioanalytical data
T min	Tmin	Time of minimum observed concentration (Cmin) following a single dose corresponding to the single IV dose administration	Taken from clinical database as the difference in the time of administration and the time of the blood draw which is associated with the Cmax
T max	Tmax	Time to reach Cmax; if Cmax occurs at more than 1 time point, Tmax is defined as the first time point with this value	Taken from clinical database as the difference in the time of administration and the time of the blood draw which is associated with the Cmax
T last	Tlast	Time of the last measurable concentration	Taken from clinical database as the difference in the time of administration and the time of the blood draw which is associated with the Clast
λ z	Kel	Apparent first-order terminal elimination rate constant	The negative of the slope of a linear regression of the log(concentration)-time curve for all concentrations > LLOQ
t ½	t½	Apparent first-order terminal elimination half-life	Calculated as $t_{1/2} = 0.693/K_{el}$

Parameter	Label to be Used in the Text, Tables, and Figures*	Definition	Method of Determination
CL	CL	Total serum clearance after IV administration	Calculated as CL = Dose/(AUC0-inf)

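### A compliant end-of-infusion sample can be drawn before the infusion ends and still be reported as Ceoi; the low bias is largely confined to that parameter and cheap to remove

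*Protocol*

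**What the plan says.** **Sampling window.** Protocol Schedule of Events, footnotes 9 (PK) and 10 (PD), place the sample at "end of the infusion (60 minutes) \pm 15 minutes". Section 6.4.1 names the same event with no window: "Serum for PD will be obtained at prior to start of infusion and then at end of infusion (60 minutes". SAP Section 6.3 lists "Predose (imputed as time 0) and approximately 1 hour", with the same window and the label "15 minutes (end of infusion [EOI".

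**Anchor.** The footnotes and Section 6.4.1 name the end of the infusion, with 60 minutes in brackets. The protocol Synopsis and Section 3.1, and SAP Sections 3 and 6.3, count 1 hour from the start.

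**Infusion.** Protocol Section 5.4: "A calibrated IV infusion pump will be set to deliver the total volume of IP over a 60-minute period", and "Start and stop times will be recorded in the subject record and eCRF". Section 5.7 says that after an infusion reaction "the infusion should be slowed or stopped and restarted at the discretion of the Investigator".

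**Parameters.** SAP Table 6-1 defines Ceoi as "Concentration at the end of infusion" and Cmax as the highest observed value. Both are read off the laboratory result with no calculation. SAP Section 6.4.1 uses actual sample times, counted from the start of infusion. SAP Section 6.5 lets concentrations more than 3% off nominal time be left out of concentration summaries and figures, at discretion.

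**The concern.** The window is symmetric, but the concentration curve around the end of an infusion is not. Before the pump stops, concentration climbs almost in proportion to the dose delivered. After it stops, concentration falls slowly. Fifteen minutes early therefore costs much more than fifteen minutes late, and the errors do not cancel.

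Using actual times protects AUC but does nothing for Ceoi or Cmax, which are observed values. No rule says what happens to Ceoi when the sample was drawn before the stop time. The mixed anchor adds to this: if an infusion runs past 60 minutes, a site following the from-start wording could draw mid-infusion and stay within the window.

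At stake is whether the reported Ceoi is what its label says. Each dose group has six active subjects, and the SAP presents Ceoi as a geometric mean with geometric CV. One draw in six at the 45-minute limit lowers that mean by about 5% (0.75^(1/6) = 0.953) and widens its CV.

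**Working it through.** The plan states no expected Ceoi or Cmax, so there is no figure to reproduce. The check sizes the error.

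**Inputs from the documents**
- Infusion T = 1 h at constant rate (protocol 5.4); window 0.75 to 1.25 h; next sample at 2 h (footnote 9).
- Rat kinetics (protocol 1.3.2): half-lives 3 h and 46 h, AUC 1,642 µg·h/mL, Cmax 184 µg/mL, used here as the initial concentration.

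**Assumed human range** (the text gives no human estimates): distribution half-life 6-48 h, terminal half-life 21 days, 40-60% of the initial concentration in the distribution phase.

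**Formulas**, with k = ln 2 / half-life:
- During infusion: C(t) = Σ aᵢ/(kᵢT) × (1 − e^(−kᵢt))
- After infusion: C(t) = Σ aᵢ/(kᵢT) × (e^(−kᵢ(t−T)) − e^(−kᵢt))

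**Rat fit.** 1/k is 4.328 h and 66.36 h. Solving A + B = 184 and 4.328A + 66.36B = 1,642 gives B = (1,642 − 184 × 4.328)/(66.36 − 4.328) = 13.6 and A = 170.4.
- C(0.75) = 737.4 × 0.1591 + 904.6 × 0.01124 = 127.5
- C(1) = 737.4 × 0.2063 + 904.6 × 0.01496 = 165.6
- Ratio = 0.77

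**Ceoi relative to its true value**

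| Draw | Rat | Assumed human |
|---|---|---|
| 45 min | 0.77 | 0.75-0.76 |
| 75 min | 0.95 | 0.98-1.00 |
| Mean, uniform 45-75 min (assumed) | 0.93 | 0.935-0.937 |

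The 45-minute loss hardly depends on the kinetics because it is mostly undelivered dose: 45/60 = 0.75. The mean has a similar hand check. Half the draws are early, with an average shortfall of about 12.5%, so ½ × 12.5% = 6.25% before any late-draw loss.

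**Cmax.** After an early draw, the larger of that value and the 2-hour value is reported. In the assumed human range C(2)/C(1) is 0.94-0.99. Averaged over a uniform window, Cmax is 0.968-0.996 of the true value, or 0.4-3.2% low.

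**AUC.** Moving the draw to 45 minutes and using its actual time changes AUClast by about −1% (rat) or less than 0.1% (assumed human, distribution half-life 12-48 h).

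**Prolonged infusion, illustrative.** If the infusion were slowed evenly to 90 minutes and the sample taken 60 minutes after the start, 60/90 = 0.67 of the dose would be in. The model gives 0.67-0.70 of the true end-of-infusion value.

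**The case against.** **What stands against the point**
- Ceoi is not a protocol endpoint. Protocol Sections 2.2.2 and 8.6 list Cmax, Cmin, CL, Vss and half-life; Ceoi appears only in the SAP, and SAP Section 6.5 mentions it conditionally.
- The 23-25% is a boundary value. Nothing suggests that a research unit using a pump would draw near the early limit.
- Early draws can be found afterwards: SAP Appendices 16.2.5.3 and 16.2.5.5 list infusion times and draw times. A 45-minute draw is 15/60 = 25% off nominal, so the 3% rule can catch it. That rule is discretionary, though, and does not mention Ceoi.
- PK is descriptive, and dose escalation (protocol Section 3.5) rests on adverse events, vital signs and laboratory results.

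**Stronger readings that the documents do not support**
- *Cmax is badly biased.* With the rat fit, the 2-hour sample is only 0.81 of the end-of-infusion value. But this carries rat bolus kinetics into humans, with 170.4/184 = 93% of the initial concentration in the distribution phase. It also misses the rat Vss. Vss = Dose × (A/α² + B/β²)/AUC², where α and β are the two rate constants, gives 10,000 × 63,226/1,642² ≈ 235 mL/kg, against 305 stated. The 10 mg/kg dose used there is itself assumed, because Section 1.3.2 gives 10 mg/mL.
- *The PD result is biased.* The PD endpoint relates concentration ranges to neutralization. An early sample gives a lower but valid pair; only its time label is wrong.
- *The sample is fixed at 60 minutes even if the infusion runs on.* Footnotes 9 and 10 and Section 6.4.1 name the end of infusion. The fault is inconsistent wording, and harm would also need a prolonged infusion and a draw taken before it ended.

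**Conclusion.** The point holds in limited form. A compliant sample can precede the end of the infusion and be reported as Ceoi, and nothing in the SAP requires otherwise. The direction is certain. The size is 23-25% low for a draw at the limit and about 6-7% low on average if draws are uniform over the window; actual draw times may do better or worse.

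The Cmax effect is about 0.4-3% on average under the assumed human range. It would be larger only if human distribution were as fast as in the rat, which the documents give no ground to assume. AUC, CL and Vss are little affected, and paired PD results are not biased. The anchor wording needs reconciling in any case.

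This merits consideration as a cheap improvement to one descriptive parameter. It does not threaten the trial's conclusions.

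**What to change.** 1. Define the PK and PD sample as 0 to +15 minutes after the actual recorded end of infusion, preferably with a shorter upper limit. Use the same wording in Schedule of Events footnotes 9 and 10, protocol Section 6.4.1 and SAP Section 6.3. Carry it into the repeated time-point lists in the protocol Synopsis and Section 3.1, SAP Section 3, and the programmer note to Table CPConc1 in SAP Section 11.3.
2. Add to SAP Table 6-1 that Ceoi is set to missing when the draw precedes the recorded stop time. If the protocol cannot be amended, this rule alone prevents mislabelled values.

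**Effect.** The worst-case Ceoi error falls from 23-25% to about 5% (rat kinetics) or 2% (assumed human range). The mean error over a uniform window falls from 6-7% to about 2.6% or less. With 0 to +5 minutes it is about 0.9% or less. A small late-draw loss remains, hence the preference for a short limit.

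**Cost.** No added sample, visit or blood volume, and stop times are already recorded. Site staff work to slightly tighter timing, and an occasional Ceoi will be missing.
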